## 10.2. Secondary Efficacy Analysis

The primary efficacy analysis will be performed on the Per Protocol population. The change from baseline in Health-related Quality of Life (HRQL) score will be summarized with descriptive statistics. The HRQL is a subset scale of 25 questions. The numbers presented represent transformed composite scores, ranging from 0-100. Boxplots with observed values and changes from baseline may also be presented. Data will be summarized at 2, 3, and 4 months of therapy a by all subjects and in each treatment arm in the per protocol population. Missing data will not be imputed for subjects that do not have HRQL scores at each given timepoint.

The reduction from baseline in number of UUI episodes per day on a 3-day diary will be summarized with descriptive statistics (n, mean, median, standard deviation, 25th quartile, 75th quartile, minimum, and maximum after 2, and 4 months of eCoin tibial nerve stimulation. The voiding diary CRF will report the total over the 3 days for each measure, which will then be averaged. Boxplots with observed values and change from baseline may also be presented for all subjects and each treatment arm in the per protocol population. Data will be summarized at 2 and 4 months of therapy. Missing data will be handled the same as for the primary endpoint.

Observed answers for the patient satisfaction survey will be pooled by question. Data will be summarized at baseline, 2, 3, and 4 months of therapy and by all subjects and each treatment arm in the per protocol population. Missing data will not be imputed for these analyses.

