**Synopsis**

|   |  |
|---|--|
| Protocol title                                   | Evaluating Effectiveness of Sensory and Subsensory Stimulation Amplitudes with eCoin® Tibial Nerve Stimulation in Urgency Urinary InContinence Episodes and Quality of Life (ESSENCE)  |
| Treatment assignment                             | Enrolled subjects will be assigned to the following treatments: 
 
• eCoin programmed at sensory level
 
• eCoin programmed at subsensory level
 
  |
| Study design                                     | Prospective, multi-center, double-blinded randomized controlled clinical trial designed to observe the effectiveness and QOL of two different programming methods for the FDA-approved eCoin device.   |
| Analysis population                              | The primary analysis population for the effectiveness outcomes will be the per protocol population. The safety analyses will be the safety population: all enrolled subjects who undergo a procedure for implantation of eCoin.  |
| Primary efficacy outcome                         | The primary endpoint is to explore the effect of two different eCoin programming methodologies on the reduction of UUI episodes per day on a 3-day voiding diary after 3 months of eCoin tibial nerve stimulation.   |
| Key (alpha-preserved) secondary efficacy outcome | The secondary endpoints are: 
 
1. Change from baseline in the patient reported quality of life as assessed by the Health-Related Quality of Life (HRQL) portion of the Overactive Bladder questionnaire (OABq) survey after 2, 3, and 4 months of therapy at two different programming methodologies.
 
2. Reduction from baseline in the number of urgency urinary incontinence episodes per day on a 3-day voiding diary (72 hours) after 2 and 4 months of eCoin tibial nerve stimulation at two different programming methodologies.
 
3. Improvement from baseline of patient satisfaction with UUI symptoms as gathered from patient satisfaction surveys after 2, 3 and 4 months of therapy at two different programming methodologies.
 
 |
| Primary safety outcome                           | Safety will be assessed by collection of adverse events related to the device and/or procedure, all serious adverse events, and device malfunctions.   |

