**Secondary Endpoints**

1. Change from baseline in the patient reported quality of life as assessed by the Health Related Quality of Life (HRQL) portion of the Overactive Bladder questionnaire (OABq) survey after 2, 3, and 4 months of therapy at two different programming methodologies.
2. Reduction from baseline in the number of urgency urinary incontinence episodes per day on a 3-day voiding diary (72 hours) after 2 and 4 months of eCoin tibial nerve stimulation at two different programming methodologies.
3. Improvement from baseline of patient satisfaction with UUI symptoms as gathered from patient satisfaction surveys after 2, 3 and 4 months of therapy at two different programming methodologies.

---

5. Study Methods

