#### **5.4. Schedule of Assessments**

The enrollment process consists of obtaining informed consent, screening, completing baseline evaluation, implanting the eCoin system, and establishing the participant's amplitude setting. Follow up assessments will occur at 2- and 3-months post activation. The patient and investigator unblinding will occur at the end of the 3 months visit and a final follow up visit will occur at 4 months post-activation. A revision procedure would not reset the initial activation date.

For visits involving a 3-day voiding diary, the diary should be completed over 3 consecutive days during the 7 days prior to the indicated visit. The timing windows associated with each visit number is described below.

- Visit 1: Screening Procedures (informed consent, demographic and medical history and concomitant medication/therapy information, physical examination, and vital signs are collected, subjects begin 2 week wash-off of OAB medications or 4 week wash-off of PTNS if applicable, eligibility determination)
- Visit 2: Baseline Assessments (3-day voiding diary, OABq, patient satisfaction survey, concomitant therapy review, final eligibility determination) (Time: Between 3 and 32 days from Visit 1)

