## Valencia Technologies Corporation

- Visit 3: Implant Procedure (vital signs collected, adverse event assessment, concomitant therapy review, pictures taken) (Time: Between 0 and 20 days from Visit 2)
- Visit 4: Incision Healing Check (vital signs collected, adverse event assessment, pictures taken, concomitant therapy review) (Time: Between 9 and 19 days from Visit 3)
- Visit 5: Initial Activation and Randomization at Sensory or Subsensory (vitals signs collected, adverse event assessment, pictures taken, concomitant therapy review) (Field Clinical Engineer present)) (Time: Between 23 and 43 days from Visit 3)
- Visit 6 (2 months post-activation): Follow-up assessments (3-day voiding diary, OABq, patient satisfaction survey, adverse event assessments, concomitant medication therapy review) (Time: Between 7 and 9 weeks from Visit 5)
- Visit 7 (3 months post-activation): Follow-up assessments (3-day voiding diary, OABq, patient satisfaction survey, adverse event assessments, concomitant medication therapy review, unblinding and reprogramming as requested (Field Clinical Engineer present)) (Time: Between 12 and 14 weeks from Visit 5)
- Visit 8 (4 months post-activation): Follow-up assessments (3-day voiding diary, OABq, end of study survey, adverse event assessments, concomitant medication therapy review) (Time: Between 16 and 18 weeks from Visit 5)

|  | Screening | Baseline | Implantation | Incision Healing Check | Activation (Follow up Clock Starts) | 2 Month | 3 Month: Primary Endpoint | 4 Month |
|--|-----------|----------|--------------|------------------------|-------------------------------------|---------|---------------------------|---------|
| Demographics, screening exam, physical exam, & medical history | X         |          |              |                        |                                     |         |                           |         |
| Eligibility Determination                                      | X         | X        |              |                        |                                     |         |                           |         |
| Informed Consent   | X         |          |              |                        |                                     |         |                           |         |

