## 8. General Statistical Conventions and Considerations

Descriptive statistics will summarize results of the ESSENCE protocol. Standard descriptive statistics, such as number of subjects, mean, standard deviation, quartiles, minimum, and maximum, will be calculated for continuous variables. For discrete variables, summary tables will display numbers of subjects and related percentages. Tables will display three columns of results showing all data as well as the sensory and subsensory treatment arms. The general statistical conventions and definitions used for the data analysis are described below.

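### The 4-month secondary results follow unblinding and optional reprogramming, yet the SAP words them as results of the programming method and repeats them in a 'blinded' subgroup

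*SAP*

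**What the plan says.** **Endpoints.** The SAP synopsis defines the secondary endpoint for urgency urinary incontinence (UUI) as the reduction "after 2 and 4 months of eCoin tibial nerve stimulation at two different programming methodologies". SAP Table 1 words the quality-of-life (HRQL) endpoint as change "after 2, 3, and 4 months of therapy at two different programming methodologies", and the satisfaction endpoint carries the same ending. The Protocol's versions of these endpoints (2-3-2-1-2) do not have that phrase.

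**Presentation.** SAP 10.2 says of HRQL: "Data will be summarized at 2, 3, and 4 months of therapy a by all subjects and in each treatment arm". UUI at 2 and 4 months and satisfaction at 2, 3 and 4 months are also shown by arm in the per-protocol (PP) set, and SAP 10.3 repeats everything in the ITT set. SAP 8 fixes the layout: "Tables will display three columns of results showing all data as well as the sensory and subsensory treatment arms".

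**Unblinding and reprogramming.** SAP 5.4 states: "The patient and investigator unblinding will occur at the end of the 3 months visit". Its entry for Visit 7 lists "unblinding and reprogramming as requested (Field Clinical Engineer present". Protocol 2-4-2 says the engineer offers reprogramming once the 3-month assessments are done.

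**Blinded subgroup.** SAP 10.4.2 takes ITT subjects whose blind held through 3 months and repeats the primary and the secondary endpoints in them, with no limit on time point.

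**Programming departures.** SAP 9.6 counts reprogramming as a departure only when it comes before 3 months. SAP 7.1, SAP 10.1 and the PP definition in Protocol 2-6-4-2 exclude programming departures without a time limit.

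**The concern.** The trial sets out to learn how the amplitude setting relates to outcome. At 2 and 3 months the arm label stands for a setting delivered under blinding. At 4 months it need not identify the setting in use, and diary and surveys are completed by patients who know their assignment. A table that runs 2, 3 and 4 months under the same arm headings invites the reader to treat the three time points as the same kind of evidence.

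The SAP applies this reasoning elsewhere. In SAP 6 it prefers the pivotal study's 8-week data to its 12-week data because patients could be reprogrammed at 8 weeks, which it regards as confounding the later results. The 4-month data here have that structure and are unblinded as well.

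The planned outputs would not let a reader judge how much this matters. Whether none or all of an arm had left its assigned setting by 4 months would not appear in any of them.

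**Working it through.** No figure in the plan addresses this point, and the precision table in SAP 6 does not enter into it. The check uses the visit windows and a comparison of sections.

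**1. Timing, in days from activation (SAP 5.4).**
- Visit 7 is at 12 to 14 weeks: 12 × 7 = 84 to 14 × 7 = 98.
- Visit 8 is "Between 16 and 18 weeks from Visit 5": 16 × 7 = 112 to 18 × 7 = 126.
- Gap from Visit 7 to Visit 8: 112 − 98 = 14 to 126 − 84 = 42 days.
- For the diary the rule is that "the diary should be completed over 3 consecutive days during the 7 days prior to the indicated visit". The earliest 4-month diary day is 112 − 7 = 105, which is 105 − 98 = 7 days after the latest in-window Visit 7. The latest diary start is 126 − 3 = 123, which is 123 − 84 = 39 days after the earliest Visit 7.

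All in-window 4-month diaries thus start 7 to 39 days after unblinding, and the surveys follow it by 14 to 42 days. There is no overlap.

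**2. How many results are touched (SAP Table 1).**
- HRQL has 3 time points, UUI 2 and satisfaction 3: 3 + 2 + 3 = 8.
- At 4 months: 1 + 1 + 1 = 3. At 2 and 3 months: 8 − 3 = 5.
- The 4-month satisfaction result is narrower than the others. The satisfaction survey is not given at 4 months (SAP 5.4 table, 5.6). Only the 1 question and 4 statements carried into the exit survey are available (SAP 5.6.3).

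**3. Is there a label or a count?**
- SAP 9.1 (disposition) has no row for reprogramming.
- SAP 9.4 lists premature unblinding only.
- SAP 9.6 names reprogramming only before 3 months. Its bullets on a device turned off and on programming deviations have no time limit, but a permitted change at Visit 7 is not a deviation.
- SAP 9.8 gives weeks implanted and weeks activated.
- SAP 10.2 to 10.4 do not mark the 4-month results as post-unblinding.

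**4. The blinded subgroup.** Its definition stops at 3 months, while the secondary endpoints it repeats run to 4 months. By step 1, none of its in-window 4-month data are blinded.

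**5. Illustration only.** The documents give no reprogramming rate, so the share p is an assumption from 0 to 100%, as is full effect of the new setting by 4 months. If p of one arm moves to the other arm's setting and the other arm stays, the difference between the two columns keeps 1 − p of the true setting difference: 90%, 75%, 50% and 0% for p = 10%, 25%, 50% and 100%. If both arms swap in equal shares it keeps 1 − 2p: 80%, 50% and 0% for 10%, 25% and 50%. The SAP plans no such 4-month contrast. This is what a reader comparing the columns would face.

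**The case against.** A fair defence has four parts.

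- **The wording is only a name for the arms.** The SAP uses the programming-methodology phrase generally, and SAP 10.2 itself says treatment arm. By-arm summaries of assigned groups are legitimate. This stands in part. A reader might infer that the SAP makes a causal or between-arm claim at 4 months, and it does not: 10.2 plans descriptive statistics only, and the confidence interval and optional effect size in 10.1 belong to the 3-month primary. The endpoint definitions still tie the 4-month results to the programming method.
- **The sequence is disclosed.** SAP 5.1 and 5.4 state when the blind ends, and SAP 8.3.2 and 8.3.3 put the 4-month results in a separate analysis with a second database lock. True, but that separates timing only. Nothing carries the fact into the outputs.
- **A missing count is an omitted table.** SAP 8.3.3 leaves its list open, so the count could be added. That stands, and it is a reason to write it in.
- **Retention in the PP set is not settled.** A reader of SAP 9.6 might infer that subjects reprogrammed at Visit 7 certainly remain in the PP set. That is the more natural reading, since the change is permitted, but SAP 7.1, SAP 10.1 and Protocol 2-6-4-2 carry no time limit. The clause giving the SAP precedence on minor differences does not resolve it, because the SAP sections themselves differ.

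**Conclusion.** The point holds as one of labelling and interpretation. Three of eight secondary endpoint-by-time results, one of them based only on the items carried into the exit survey, describe originally assigned arms after unblinding and open choice of setting. The firmest error is SAP 10.4.2, which as written produces 4-month results for a blinded population from unblinded data.

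A reader might infer that the 3-month primary or the 2- and 3-month secondary results are compromised. The documents do not support that if the time limit in SAP 9.6 governs the PP set. Only a literal, unlimited reading of SAP 7.1 or Protocol 2-6-4-2 could remove subjects from the 3-month PP analysis for a change made after their 3-month data were collected. That is why the definitions need reconciling.

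The timing conclusion assumes that Visit 7 took place in its window. A late or missed Visit 7 could be an exception. The size of any effect at 4 months cannot be derived. With no pass/fail criteria and no powered comparison (SAP 5.1, 10.1), no trial decision depends on it, but the correction should be made because it changes what the 4-month results can be said to show.

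**What to change.** 1. In SAP 10.4.2, limit the blinded-subgroup analysis to endpoints through 3 months.
2. In the SAP synopsis, Table 1, 8.3.3, 10.2 and 10.3, label the 4-month results as open-label, post-unblinding summaries by originally assigned arm.
3. In the end-of-study analysis, report per arm the number of subjects reprogrammed at the 3-month visit.
4. Reconcile SAP 7.1, SAP 10.1 and Protocol 2-6-4-2 with SAP 9.6 on whether reprogramming permitted at Visit 7 affects PP membership.

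The cost is wording edits and one added count per arm. The SAP schedule already has programming at the 3-month visit and Protocol 2-6-1 lists a Programming form, so the count should need no new collection. The form's fields are not shown, and if it does not record the 3-month setting, one field is needed. SAP 8.4 asks for such changes in a revised plan before database lock and the primary analysis. No change to unblinding, reprogramming or the visit schedule is proposed.

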## 10.3. Sensitivity and Additional Analysis

The primary and secondary efficacy analysis will be repeated the ITT population. There is no planned sensitivity analysis for missing data.

## 10.4. Exploratory Subgroup Analysis

### 10.4.1. Responders

The proportion of subjects who respond to treatment (achieve at least a 50% reduction from baseline in the number of UUI episodes per 24 hours on a 3-day voiding diary after 3 months of eCoin tibial nerve stimulation) will be summarized for all subjects, the sensory arm, and subsensory arm from the per protocol population.

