- Some subjects may not receive clinical benefit from eCoin therapy in either arm; however, the expectation is that subjects will continue with the trial, at least until the primary endpoint, regardless of response. Some individuals who initially do not receive clinical benefit may benefit from late response and cumulative effects of treatment.
- At unblinding, subjects will be offered reprogramming if desired.
- Subjects are intended to be without pharmacological medications for overactive bladder. If the addition of medications is medically necessary as described herein, such information will be collected and reported.

2-4 Study Procedures

All subjects will be followed for up to 4 months post-activation. A 3-day voiding diary will be collected that reports the number and type of incontinence episodes. Subjects will be administered questionnaires including the OABq and patient satisfaction surveys at 2, 3, and 4 months post-activation.

The follow-up study visits are described in relationship to the initial activation visit occurring about 4 weeks after implantation of the study device. See Visit Overview 2-4-2 for exact timing of such visits. For any enrolled subject who is not activated, the same schedule will be followed as if the subject were activated.

Subjects should avoid concomitant therapies, including OAB medications, onabotulinumtoxinA, PTNS or TENS therapies, until the primary endpoint at 3 months. If taken, these therapies will be recorded and noted in the results. Subjects who are taking pharmacologic medication at screening should be washed off OAB medications for a period of 2 weeks prior to filling out the baseline diary.

All subjects will exit from the study after the last study visit at 4 months post activation. Patients may retain their device and remain under the care of their implanting physician.

COVID-19 Considerations

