2-6-7 Missing Outcome Data

Because this study is investigating an implanted device, nearly all implanted patients are expected to have data on the primary and secondary endpoints. Careful clinical planning that minimizes patient dropouts will be implemented. Missing data imputations will not be performed.

The SAP will provide further details on handling missing data for the secondary outcomes.

2-6-7-1 *Concomitant Therapies*

Concomitant therapies are prohibited until the primary endpoint at 3 months.

2-6-8 Safety Analysis

All device- and procedure-related adverse events and SAEs up to 4 months after activation will be summarized. Tabulations of these data will include the number of subjects exposed and the number of subjects with at least one device- or procedure-related adverse event. Tabulations of device- and procedure-related AEs and SAEs which will be provided by time point, will include the number of (S)AEs, the number of subjects who experienced the S(AE), and the percent of subjects who experienced the S(AE).

2-7 Data Handling, Record Keeping and Study Monitoring

2-7-1 Confidentiality and Security

The Investigator will ensure that the subject's confidentiality is maintained on the CRFs or other documents submitted to the Sponsor. Subjects should be identified by their initials and a subject study number only. Documents that are not for submission to the Sponsor, such as the signed informed consent forms, should be kept in strict confidence by the Investigator. In compliance with ICH GCP Guidelines, the Investigator and institution are required to permit authorized representatives of the company, of any relevant regulatory agency, and the IRB direct access to review the subject's original medical records for verification of study-related procedures and data. Direct access includes examining, analyzing, verifying, and reproducing any records and reports that are important to the evaluation of the study. The Investigator will inform and obtain the consent of the subject to permit named representatives to have access to his/her study- related records without violating the confidentiality of the subject. Information about study subjects will be kept confidential and managed according to the requirements of the clinical sites regulatory authority. As a part of the consent process, subjects will sign an authorization informing the following:

- What protected health information (PHI) will be collected from subjects in this study

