## 6. Sample Size Determination

This study will explore the effect of two programming methodologies (sensory and subsensory amplitude) on reduction of UUI episodes per day as compared to baseline. Change of average UUI per day at 3-months follow-up will be summarized with descriptive statistics for each study arm.

As detailed below, the minimum sample size required for this study is 32 subjects (16 per arm). The planned enrollment of 40 subjects implanted and up to 50 meets this minimum. From the pivotal study, a total of n=133 patients were implanted with eCoin. Looking at the subset of patients programmed at or below sensory level, after 8 weeks of therapy there was a mean reduction in UUI episodes of 2.3 with a standard deviation of 1.4, After 12 weeks of therapy, there was a mean reduction in UUI episodes of 2.7 with a standard deviation of 1.8 per day (n=22). Based on a confidence interval using a t-distribution, a two-sided type-I error rate of 0.05, and using a standard deviation of 2, precision was calculated for a range of sample sizes using the equation below based on the PASS One Mean Module with Tolerance Probability. Margin of error, also known as precision, is the distance between the mean and edge of an interval.

$$D = \frac{t_{1-\alpha/2, n-1} * \hat{\sigma}}{\sqrt{n}}$$

| Sample Size | Precision |
|-------------|-----------|
| 13          | 1.21      |
| 14          | 1.15      |
| 15          | 1.11      |

|    |      |
|----|------|
| 16 | 1.07 |
| 17 | 1.03 |
| 18 | 0.99 |
| 19 | 0.96 |
| 20 | 0.94 |

\*Standard deviation=2

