We plan to use the per protocol population as our primary analysis population. This is due to the concern that the Intent to Treat (ITT) population will be diluted due to deviations from the assigned therapy. To adjust for noncompliance/nonadherence, we must estimate the proportion from the subsensory group who will have a sensory level that is cannot be reduced by 25% (i.e. their sensory threshold is the minimum setting of 0.5 mA). Based on the Pivotal trial, 3.85% (n=130) had a sensory threshold of 0.5 mA. Since this scenario only affects the subsensory arm, we estimate this this proportion to be 0.02. Additionally, in the subsensory threshold group, we must adjust for patients who have no sensory threshold, (i.e. they do not feel sensation at any amplitude level and therefore are unable to identify the sensory setting). Based on the Pivotal trial, 6.15 % (n=130) had a sensory threshold of “not identified.” Since this scenario only affects the sensory arm, we estimate this scenario to be 0.03. Lastly, we plan for a 10% dropout rate.

[figure not shown]
Considering the scenarios described above, a sample size of n=16 will have a precision of 1.07. For this analysis, we are considering a low assumed treatment effect as a mean reduction of 1.3. This is the 3rd quartile of mean reduction from the pivotal trial at 2 months, meaning 75% of the data lies below -1.3. The mean reduction from 8 weeks is being used for this analysis because in the pivotal study, patients had the option to reprogram at 8 weeks, therefore the 12 week results are confounded by reprogramming. Since the precision of 1.07 is below our assumed treatment effect of 1.3, the confidence interval (0.23, 2.37) does not include zero. This means if the treatment is effective, we expect to have sufficient sample size to see a result. Accounting for 15% of patients taken out of the Per Protocol population due to withdrawal or deviations from the assigned therapy group, a sample size of 13 per arm has a precision of 1.21 which is less than 1.3 UUI.

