## 10. Efficacy Analysis

### 10.1. Primary Efficacy Analysis:

This randomized controlled double-blind study will evaluate the efficacy of eCoin in reducing episodes of UUI per day with two different treatment arms. The primary efficacy outcome is the reduction from baseline in the number of UUI episodes per day on a 3-day voiding diary (72 hours) after 3 months of eCoin device tibial nerve stimulation. The voiding diary CRF will report the total over the 3 days for each measure, which will then be averaged.

The primary efficacy analysis will be performed on the Per Protocol population. The change from baseline will be summarized with descriptive statistics (n, mean, median, standard deviation, 25th quartile, 75th quartile, minimum, and maximum). Additionally, the mean reduction of UUI episodes per day along with its two-sided 95% confidence interval will be summarized for all subjects, sensory arm, and subsensory arm. Boxplots and line graphs with observed values and change from baseline may also be presented. Treatment effect size may be reported using Cohen's d and/or relative risk to highlight the observed differences, if any.

No data imputations will be performed for subjects who do not have 3-month post-activation data. Missing and incomplete diary data will be handled per section 8.6.3 Missing or Incomplete Diary.

The primary endpoint is exploratory in nature. There are no pass/fail criteria to define the study success and there is no powered comparison between the two treatment arms

Because this study is exploring the efficacy of the eCoin System programmed using two different methodologies, the per protocol population will be analyzed for the primary endpoint. The per protocol population, as described in section 7. Analysis Populations, will exclude patients that have taken OAB medications, do not meet eligibility criteria, experience major protocol deviations and/or experience departures

from the assigned programming treatment. Due to the nature of the study, it is expected a subset of all implanted subjects will have data on the primary endpoint.

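### OAB-drug users drop out of the only planned responder denominator, and no planned analysis counts drug use as an unfavourable outcome

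*SAP*

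**What the plan says.** **Drug use is foreseen.** Protocol 2-3-4 intends subjects to be off OAB drugs but allows for additions: "If the addition of medications is medically necessary as described herein, such information will be collected and reported". Protocol 2-4 asks subjects to avoid such therapies up to month 3 and says that any use will be noted in the results. Protocol 2-6-7-1 is stricter: "Concomitant therapies are prohibited until the primary endpoint at 3 months". These passages need reconciling, but none says how drug use enters an estimate.

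**Per-protocol set (primary).** Protocol 2-6-4-2 requires subjects to be free of OAB drugs and names no period. SAP 7.1 extends the condition over the whole study. SAP 10.1 says the set "will exclude patients that have taken OAB medications, do not meet eligibility criteria, experience major protocol deviations and/or experience departures" from the assigned programming.

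**Responders.** The proportion with at least a 50% reduction at month 3 "will be summarized for all subjects, the sensory arm, and subsensory arm from the per protocol population" (SAP 10.4.1). No second version is planned.

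**ITT set.** SAP 7.2 requires implantation, randomisation, and baseline and month-3 data, with no condition on drugs. SAP 10.3 states: "The primary and secondary efficacy analysis will be repeated the ITT population". The responder proportion is exploratory and is not on that list. The blinded subgroup (SAP 10.4.2) is drawn from ITT and inherits the same handling.

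**The concern.** Starting an OAB drug happens after randomisation and may reflect poor control at the assigned amplitude. The plan deals with it in two ways: per-protocol removes the subject, and ITT takes the on-drug diary at face value against a baseline taken after drug washout. Neither records that the subject needed something besides the device.

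The reason given for a per-protocol primary analysis is that departures from the assigned therapy would dilute ITT (Protocol 2-6-5, SAP 6). That reason does not reach drug use. Adding a drug is not a change of amplitude, and the list of programming departures in SAP 9.6 leaves it out.

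Two things are at stake. The responder rate is the figure by which Protocol 1-5 summarises the earlier eCoin studies (65%, 82% and 68%), so readers will set this trial's rate beside those. The trial also exists to look at two programming levels, and SAP 10.1 allows Cohen's d or a relative risk to describe the difference. With about 20 subjects per arm, a few exclusions that differ between arms can move that contrast.

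There is also a timing problem. Read literally, SAP 7.1 removes a subject from the month-3 result because of a drug started after month-3 unblinding, although Protocol 2-4 asks for avoidance only until then. The primary analysis runs once all subjects reach month 3 (SAP 8.3.2), so membership of its own analysis set could still change by month 4.

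**Working it through.** **1. The plan's own figures.** SAP 6 uses "a two-sided type-I error rate of 0.05" and computes precision "using a standard deviation of 2", with D = t(0.975, n−1) × SD / √n.
- n = 16: D = 1.066, stated as 1.07.
- n = 13: D = 1.209, stated as 1.21.
- All eight tabulated values reproduce to within 0.01, and 1.3 ± 1.07 = (0.23, 2.37).
- The loss allowance is 2% + 3% + 10% = 15%, and 16 × 0.85 = 13.6, taken as 13. None of the three parts is for OAB-drug use.

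The precision figures stand. They are silent on drug use, so its effect has to be illustrated.

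**2. Responder rate in one arm.** Assumptions: N = 20 (half the planned 40), r = 12 responders, all drug-free, and k users who would not have responded unaided. Per-protocol gives r/(N−k). Counting users as non-responders gives r/N.

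| k | Per-protocol | Users as non-responders |
|---|---|---|
| 1 | 12/19 = 63.2% | 12/20 = 60% |
| 2 | 12/18 = 66.7% | 60% |
| 3 | 12/17 = 70.6% | 60% |
| 4 | 12/16 = 75.0% | 60% |

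Alternatively, hold the rate among drug-free subjects at 68%, the pivotal figure at 48 weeks (Protocol 1-5). Per-protocol then stays at 68% for every k. Counting users as non-responders gives 0.68 × (20−k)/20 = 64.6%, 61.2%, 57.8% and 54.4% for k = 1 to 4.

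**3. Contrast between arms.** Assume 1 user in the sensory arm and 4 in the subsensory arm.
- *A difference is hidden.* 12/20 against 10/20 is 60% against 50%, a ratio of 0.83. Per-protocol shows 12/19 = 63.2% against 10/16 = 62.5%, a gap of 0.7 points and a ratio of 0.99.
- *A difference is created.* 12/20 in each arm is no difference. Per-protocol shows 12/19 = 63.2% against 12/16 = 75.0%, a gap of 11.8 points in favour of the arm with more drug use.

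**4. Mean change.** Assumptions: N = 20, k = 4, and non-users at a mean reduction of 2.3 (the pivotal 8-week figure in SAP 6). As a reference for users, take the plan's low value: "we are considering a low assumed treatment effect as a mean reduction of 1.3".
- Per-protocol: 2.30.
- ITT, users on drug at 1.3 to 2.3: (16 × 2.3 + 4 × 1.3)/20 = 2.10, up to 2.30.
- Value had users stayed off drug, at 0 to 1.3: (16 × 2.3 + 4 × 0)/20 = 1.84, up to (16 × 2.3 + 4 × 1.3)/20 = 2.10.

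Per-protocol lies above the off-drug value only because users were assumed to do worse than non-users. ITT lies above it only where the drug improves the diary. If users reach 1.3 with or without the drug, both ITT and the off-drug value are 2.10 and ITT has no bias.

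**The case against.** A reader might infer more than the documents support, in three ways.

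- *Both planned analyses err upward.* For the ITT mean this needs the drug to work. Protocol 2-4-4 says the study means to enrol patients whose condition has not yielded to other treatment, drugs included. If users still do badly on drug, ITT keeps their poor diaries and falls below per-protocol, as a sensitivity set should. A drug effect is not ruled out either: inclusion criterion 6 also admits people who merely could not tolerate one listed therapy. The direction is open.
- *The amplitude causes the drug use.* The documents give no rate, reason or imbalance. They expect subjects to continue to the primary endpoint whatever their response (Protocol 2-3-4).
- *The arm difference shrinks.* It can equally be created, as the working shows.

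The size of the illustration can also be questioned. Four users in 20 is 20%, more than the 15% the plan allows for all losses together. The approximate 95% half-width for 60% against 50% at 20 per arm is 1.96 × √(0.6 × 0.4/20 + 0.5 × 0.5/20) = 31 points, so a 10-point difference could not be resolved anyway. The study is descriptive, with no success criterion and no powered comparison, and the responder table is exploratory. Drug use will be noted in the results, and SAP 9.1 shows the size of each set by arm.

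These objections limit how much hangs on the point. They do not answer it. A general promise to note drug use is not a count by arm beside the result, and still no analysis treats it as unfavourable.

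**Conclusion.** The concern holds for the responder proportion. Users leave the per-protocol denominator, no other version is planned, and no planned analysis counts drug use against the device. If users would not have responded unaided, the per-protocol rate is too high by arithmetic: 3 to 15 points above 60% for one to four users in 20. Unequal use can hide a 10-point difference or produce one of 11.8 points. All of this rests on assumed numbers of users.

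For the means the claim is weaker. The per-protocol mean is too favourable only if users would have done worse off drug than non-users, and the ITT mean only if the drug improves the diary. Neither is established. The whole-study drug-free condition in SAP 7.1 is a separate defect in the text and needs no assumption.

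This is a worthwhile, inexpensive improvement to an exploratory plan. It does not invalidate the primary analysis.

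**What to change.** Keep the per-protocol analysis as planned, and make three changes.

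- **SAP 10.3 and 10.4.1.** Add a responder proportion by arm over all randomised, implanted subjects with a baseline diary. Count anyone who started an OAB drug before completing the month-3 diary as a non-responder, including users with no month-3 diary. The ITT set in SAP 7.2 will not serve, because it drops users who lack month-3 data. State the number of other subjects with missing month-3 data and how they enter the table.
- **Beside the per-protocol result.** Show the number of drug users by arm.
- **SAP 7.1.** For the month-3 endpoint, apply the drug-free condition only up to the month-3 diary, so that a drug started after unblinding does not remove a subject from that result.

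Setting a user's month-3 change to zero is not recommended. It replaces an observed diary with an arbitrary value.

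The cost is SAP wording and a few table rows. The data come from the Concomitant Medications CRF (Protocol 2-6-1) and the review at each visit. The new responder figure may be lower than the per-protocol one. SAP 8.4 asks for such changes before database lock and unblinding; after lock they would be labelled exploratory.
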